3.4 Efficacy Assessment

The ITT Population will be the primary population for the efficacy analysis. Efficacy will also be analyzed in the FAS, mITT Population, mITT On-Treatment Population, and PP Population as supportive analyses.

3.4.1 Primary Efficacy Endpoints

Primary Analysis

The primary efficacy endpoint is the percentage change from Baseline to Day 84 in LDL-C in the obicetrapib group compared to placebo group.

The LDL-C values measured by preparative ultracentrifugation (PUC) will be used. If the latter is not available, the LDL-C values will be assumed missing.

All the analysis for primary efficacy endpoint will be repeated with LDL-C values calculated as follows:

1. LDL-C will be calculated using the Friedewald equation unless triglycerides ≥ 400 mg/dL or LDL-C ≤ 50 mg/dL; where, LDL-C level will be measured directly by PUC.
2. LDL-C will be calculated using the Martin-Hopkins equation unless triglycerides ≥ 400 mg/dL or LDL-C ≤ 50 mg/dL; where, LDL-C level will be measured directly by PUC.

Primary Estimand

To assess the primary efficacy endpoint, the primary estimand is defined by the following key attributes:

- **Treatment:** obicetrapib versus placebo
- **Target Population:** participants who are randomized into the study
- **Analysis Population:** The ITT Population
- **Intercurrent events:** treatment discontinuation, prohibited medication use

- **Analysis set and handling of intercurrent events:** Treatment policy strategy will be used. All available values of LDL-C at Baseline and Day 84 will be included in the calculation of the percentage change from Baseline to Day 84.
- **Population level summary:** The difference in LS mean percentage change in LDL-C from Baseline to Day 84 between treatment groups

The analysis of covariance (ANCOVA) model with a fixed effect for the treatment group and covariates of Baseline LDL-C will be used to analyze the primary efficacy endpoint. The least squares (LS) mean, standard errors, and 2-sided 95% confidence intervals for each treatment group and for the mean difference compared to placebo will be estimated. The model will be fit assuming unequal variances for each treatment group. If substantial deviations from the model assumptions are observed, then supportive analyses, such non-parametric assessments, will be considered.

Missing data will be imputed for the primary efficacy analysis based on a pattern mixture model that uses a multiple imputation technique analyzed with ANCOVA with pre-specified fixed factors and covariates. If appropriate, based on the number of retrieved dropouts, missing measurements of non-retrieved dropouts will be modeled by known measurements from retrieved dropouts (ie, participants who remain in the study after treatment discontinuation) in the same treatment group. If the number of retrieved dropouts is such that the model convergence is questionable and the given parameter estimates cannot be obtained, then missing data at the Day 84 assessment will be estimated based on the placebo treatment group as described in subsequent sections of the SAP corresponding to the first sensitivity analysis.

Missing data at Day 84 will be imputed using a retrieved dropout imputation model assuming the data are missing not at random (MNAR). At Day 84, the data will be split into two groups as follows: (1) all participants that did not discontinue treatment and had a non-missing value at Day 84; and (2) either participants that had a missing value at Day 84, or participants that had discontinued treatment and had a non-missing value at Day 84. For the second group, 100 data sets will be imputed. The variables for the imputation model will consist of the LDL-C values from Baseline and Day 84, along with treatment group. Each data set will be combined with the first group to obtain 100 imputed data sets with no missing values at Day 84. For each imputation data set, the percent change from Baseline to Day 84 will be analyzed using the ANCOVA model described above. The results of these 100 analyses will be combined to construct the treatment estimates using the parameter estimates and associated standard errors. Similarly, the difference of the adjusted treatment means (obicetrapib vs. placebo) will be presented with the associated standard error and two-sided 95% confidence interval. Randomly chosen seed numbers will be selected for the analysis and will be retained.

Sample SAS code is shown below:

1.1

Note: Missing value imputation only using participant group (2): participants that had a missing value at Day 84, or participants that had discontinued treatment and had a non-missing value at Day 84

TREATMENT = 0 (Placebo), 1 (Obicetrapib)

LDLC_BASE = Baseline LDL_C value

LDLC_Day84 = LDL_C value at Day 84

```
*****  
proc mi data=LDL_C seed=154264 n impute=100 out= LDL_C_IMP;  
  class TREATMENT;  
  monotone method=reg;  
  var TREATMENT LDLC_BASE LDLC_DAY84;  
run;  
*****
```

1.2

```
*****  
*****
```

Note: LDL_C_IMP dataset must be merged with dataset containing participants from group (1): participants that did not discontinue treatment and had a non-missing value at Day 84.

Note: For each imputation dataset, the percentage change from Baseline to Day 84 will be analyzed using an ANCOVA approach with a fixed effect for the treatment group and covariates of Baseline LDL-C.

TREATMENT = 0 (Placebo), 1 (Obicetrapib)
BASE = Baseline LDL_C value
PCHG = Percent change from Baseline to Day 84

```
*****  
*****
```

proc mixed data= TEMP;
 by _imputation_;
 class TREATMENT ;
 model PCHG = TREATMENT BASE / ddfm=satterth solution cl;
 repeated / group=TREATMENT;
 lsmeans TREATMENT / cl diff;
run;

1.3

```
*****  
*****
```

Note: MI Analyze to combine imputations.

```
*****  
*****
```

proc mianalyze parms(classvar=full)=mixLSM;
 class TREATMENT;
 modeleffects TREATMENT;
 ods output parameterestimates=mi_LSM;
run;

proc mianalyze parms(classvar=full)=mixDIFF;
 class TREATMENT;
 modeleffects TREATMENT;
 ods output parameterestimates=minus_mi_DIFF;
run;

```
*****
```

Sensitivity Analyses

The first sensitivity analysis will be performed imputing missing LDL-C values at Day 84 based on the assumption the data are MNAR using a control-based pattern mixture method. At Day 84, the data will be split into two groups as follows: (1) all participants randomized to the obicetrapib treatment group that had a non-missing value at Day 84; and (2) either participants randomized to the placebo treatment group, or participants that had a missing value at Day 84. For the second group, 100 data sets will be imputed. The variables for the imputation model will consist of the

LDL-C values from Baseline and Day 84. In this manner, missing data at the Day 84 assessment will be estimated from the placebo treatment group. Each data set will be combined with the first group to obtain 100 imputed data sets with no missing values at Day 84. For each imputation data set, the percent change from Baseline to Day 84 will be analyzed using the ANCOVA model described above. The results of these 100 analyses will be combined to construct the treatment estimates using the parameter estimates and associated standard errors. Similarly, the difference of the adjusted treatment means (obicetrapib vs. placebo) will be presented with the associated standard error and two-sided 95% confidence interval. Randomly chosen seed numbers will be selected for the analysis and will be retained.

The second sensitivity analysis will be performed using a tipping point approach in the following steps [6-7]:

1. The missing data will be imputed using multiple imputation assuming MAR with a shift parameter in each treatment group.
2. The multiply imputed data will be analyzed using a standard multiple imputation method combining rule (Rubin's Rule).
3. Step 1 and 2 will be repeated such that the shift parameter for each treatment group will be increased in the negative and /or positive direction by a certain amount in each step until the “tipping point” is reached (i.e., where statistical significance is lost). The more the tipping point diverges from the observed data, the more robust the conclusions from the primary analysis.

The same analysis method as specified for primary analysis will be applied when analyzing adjusted data generated under each plausible shift parameter.

The third sensitivity analysis will be performed using the ANCOVA model from the primary analysis for the ITT Population using only observed cases with no imputation for missing data.

Supplemental Analyses

Supplemental analyses will be performed for the primary efficacy endpoint in order to assess any differences with the results from the primary analysis and investigate what effect, if any, protocol violations have on the trial results. In the first supplemental analysis, a mixed model for repeated measures (MMRM) approach will be utilized. The LDL-C values measured by preparative ultracentrifugation will be used. The analysis will include fixed effects for treatment group, visit, and treatment-by-visit interaction, along with covariates of the Baseline LDL-C value as a continuous covariate. The restricted maximum likelihood estimation approach will be used with an unstructured covariance matrix. The LS mean, standard errors, and 2-sided 95% confidence intervals for the treatment group and for the comparison of the treatment group to the placebo group will be provided. The MMRM approach will include all available assessments of percent change in LDL-C from Day 1, Day 30, Day 84, Day 180, Day 270, and Day 365. The model assumes that the data are missing at random (MAR). For missing data, the model will use all information from the other time points to estimate the mean treatment difference at the given time point. No imputation of missing data will be performed. The analysis will be conducted for ITT Population.

The analysis will be implemented using SAS® Proc Mixed. The sample SAS code can be found below:

.....

Note:

USUBJID = unique participant identifier
TREATMENT = 0 (Placebo), 1 (Obicetrapib)
VISIT = visit
LDLC_BASE = Baseline LDL_C value
PCHG = Percent change from Baseline

```
proc mixed;
  class USUBJID TREATMENT VISIT CVRISK STATIN;
  model PCHG = TREATMENT LDLC_BASE VISIT TREATMENT*VISIT / solution cl;
  Repeated VISIT / TYPE=UN sub=USUBJID;
  lsmeans VISIT*TREATMENT / cl diff;
run;
```

Additional supplementary analysis will be performed using the ANCOVA model from the primary analysis based on the FAS, mITT, mITT On-Treatment, and PP populations. No imputation for missing data will be performed for the analysis.

Secondary Estimand

A secondary estimand will be assessed for the primary efficacy endpoint. The secondary estimand is defined by the following key attributes:

- **Treatment:** obicetrapib versus placebo
- **Target Population:** participants who are randomized into the study
- **Analysis Population:** The ITT Population
- **Intercurrent events:** treatment discontinuation, prohibited medication use
- **Analysis set and handling of intercurrent events:** A hypothetical strategy will be used. All available values of LDL-C at Baseline and Day 84 will be included in the calculation of the percentage change from Baseline to Day 84.
- **Population level summary:** The difference in LS mean percentage change in LDL-C from Baseline to Day 84 between treatment groups.

This hypothetical estimand represents the treatment effect of obicetrapib relative to placebo at Day 84 in the randomized participants had they remained on their randomized treatment for the entire planned treatment period. This estimand uses a hypothetical strategy to handle intercurrent events and is intended to provide an estimation of the achievable study treatment effect if participants take the treatment as planned. The resulting missing values (corresponding to unobserved values or excluded values following study drug discontinuation or the use of prohibited medication) will be implicitly handled by using a MMRM approach under the assumption of missing at random. The model will be similar to the MMRM approach described previously for the supplemental analysis of the primary efficacy endpoint. The supplementary analysis for the primary efficacy endpoint assessed by secondary estimand will be performed using the mITT On-Treatment populations.

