7. A single 12-lead ECG will be performed in the supine position after 10 minutes of rest.
8. Participants must fast for a minimum of 8 hours prior to samples being collected.
9. Samples should be collected prior to study drug administration.
10. Urinalysis will be performed locally by dipstick analyses from a sample of mid-stream urine. In case of abnormal results, microscopy and other assessments will be performed at the local laboratory and the abnormality recorded as an AE.
11. A PK sample will be collected prior to study drug administration for trough measurement of obicetrapib in plasma. At Visits 2, 5, and 7, participants should take study drug after a trough PK sample has been drawn.
12. The PK sample at Visit 4 is not designated in the protocol, however the PK will be assessed using residual serum from the Day 84 limited chemistry panel to confirm patients are taking IP.

AE = adverse event; ApoA1 = apolipoprotein A1; BMI = body mass index; CV = cardiovascular; ECG = electrocardiogram; EOS = End of Study; EOT = End of Treatment; ET = Early Termination; FSH = follicle-stimulating hormone; hsCRP = high sensitivity C-reactive protein; Lp(a) = lipoprotein (a); PK = pharmacokinetic(s); TSH = thyroid-stimulating hormone; UACR = urine albumin-creatinine ratio; UPCR = urine protein-creatinine ratio; V = Visit.

2.2.2 *Sample Size Determination*

Enrollment of approximately 300 participants globally is planned for this study.

Assuming an approximate 5% drop out rate, approximately 285 participants will be evaluable for efficacy. This sample size of at least 285 evaluable participants will provide more than 90% power to detect a 30% reduction of LDL-C (standard deviation 15%) levels in the obicetrapib group compared to the placebo group at a 1-sided significance level of 0.025. This sample size will also contribute to sufficient participant exposure and safety data.

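### Does the primary retrieved-dropout imputation need a fixed minimum count, given that its convergence trigger does not fit the coded regression?

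*SAP*

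**What the plan says.** SAP 3.4.1 sets out the primary missing-data method in two steps. The first is a gate: "If appropriate, based on the number of retrieved dropouts, missing measurements of non-retrieved dropouts will be modeled by known measurements from retrieved dropouts". Protocol 9.2.1.1 carries the same gate and leaves the detail to the SAP. The second is the fallback, which opens "If the number of retrieved dropouts is such that the model convergence is questionable and the given parameter estimates cannot be obtained" and then hands over to the placebo-based method of the first sensitivity analysis. Of that method the SAP says: "In this manner, missing data at the Day 84 assessment will be estimated from the placebo treatment group".

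The imputation step runs on one subset: "either participants that had a missing value at Day 84, or participants that had discontinued treatment and had a non-missing value at Day 84". Within it, only retrieved dropouts have an observed Day 84 value, so they alone determine the fit. A Day 84 value without preparative ultracentrifugation joins the missing ones: "If the latter is not available, the LDL-C values will be assumed missing".

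The sample code uses "monotone method=reg" with "var TREATMENT LDLC_BASE LDLC_DAY84". SAP section 7 leaves detailed programming specifications to a separate document.

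**The concern.** Two things look wrong. Neither document states how many retrieved dropouts are enough, who decides, or when. And the one concrete trigger speaks of convergence, while the coded step is a least-squares fit followed by a random draw, with nothing to iterate. The mixed-model ANCOVA does iterate, but on all randomized participants, so its convergence hardly depends on the number of retrieved dropouts.

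Read literally, the trigger lets through a fit that runs but is almost uninformative. This is the confirmatory test, and under the fixed sequence in SAP 3.4.2 all the secondary tests depend on it: 2 + 3 + 3 + 3 + 2 + 3 + 3 = 19. A trial with ample power could miss its primary endpoint because a handful of people supplied the imputation model. The sensitivity analyses would reveal the instability but would not restore the formal test.

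**Working it through.** **The plan's own figure.** SAP 2.2.2 states: "Assuming an approximate 5% drop out rate, approximately 285 participants will be evaluable for efficacy". 300 × 0.95 = 285, or 190 and 95 at 2:1. With a difference of 30 and SD 15, the standard error is 15 × √(1/190 + 1/95) = 1.88, and 30/1.88 is about 16. Power is effectively 1, consistent with the stated figure of more than 90%. With all 300 observed, the SE is 15 × √(1/200 + 1/100) = 1.84.

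**When the coded regression can be fitted.** It has three coefficients (intercept, treatment, baseline). With r retrieved dropouts in total, residual df = r − 3.

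- r = 3 or fewer: no residual df, so the draw cannot be made.
- An arm with no retrieved dropouts: the treatment coefficient is not estimable.
- r = 4, both arms represented: 1 df. Estimates are returned.
- r = 5: 2 df. r = 6: 3 df.

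The residual variance is drawn as the residual sum of squares divided by a chi-square on r − 3 df. The reciprocal of a chi-square has a finite mean only from 3 df upward, which explains the instability at 4 and its rapid disappearance.

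**Size of the loss if only the second sentence operated.** Simulation used 2,000 trials per setting, 200:100, true difference −30, SD 15, 100 imputations, ANCOVA with arm-specific variances, and Rubin pooling. Assumed, because the documents do not give them: no retained effect off drug; baseline LDL-C mean 120, SD 35, at least 70 mg/dL. The row entries are the share of trials with a non-significant primary result, with both arms represented.

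| Retrieved | 3 missing | 6 missing | 15 missing | 30 missing | Median SE, 15 missing |
|---|---|---|---|---|---|
| 4 | 18-19% | 29-30% | 46-49% | 65-67% | 12.7-13.9 |
| 5 | 0.2% or less | 0.4% or less | about 2% | 6-8% | 3.1-3.4 |
| 6 | 0-0.1% | 0-0.1% | 0-0.1% | 0.2-0.7% | 2.5-2.7 |
| Fallback | 0% | 0% | 0% | 0% | 1.98 |

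A separate simulation (300 trials per setting, baseline SD 40) agrees. With 15 missing it gave 45-49% non-significant at 4 retrieved (median SE 12.2 to 14.0), 0.3% at 4+1 (obicetrapib + placebo) and 0% at 4+2. With the SD among retrieved dropouts doubled to 30, the losses were 70% at 3+1, 11% at 4+1 and 1% at 4+2.

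**Bias.** With 15 missing, the median estimate is −28.0 to −28.2 at 4 retrieved and −28.0 under the fallback. The loss is of precision only.

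**How many missing.** 5% of 300 is 15, but the SAP attaches no time point to the 5%, and Day 84 comes early in a 365-day treatment period. Protocol 4.3 keeps participants in visits after they stop drug, and SAP 3.1.8 describes retention efforts. Fifteen missing at Day 84 is therefore more likely high than low.

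**Price of a fixed cut-off.** As an illustration only, let the retrieved-dropout count be Poisson with mean 4, 6 or 8, split 2:1. If the fallback applies below 4 or with an empty arm, it is used in 51%, 23% and 10% of trials. With a minimum of 5 these become 66%, 34% and 14%; with a minimum of 6, 80%, 48% and 22%. The methods can also differ in the estimate. With 10 of 200 missing on obicetrapib, placebo-based imputation gives −30 × 190/200 = −28.5. Retrieved-dropout imputation gives −28.5 to −30.0, depending on whether retrieved dropouts keep none or all of the effect.

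**The case for a change.** The best case for a change is that the opening condition is too vague to rely on. Nobody is named to apply it and no time is set. If the analyst fits the model, sees a standard error of 13 and then calls the model inappropriate, that switch is open to challenge. One sentence with a number would close the question cheaply, in the analysis that gates everything else.

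Part of this stands. A number would be tidier, and the word convergence is badly chosen for this code. But the step from untidy to harmful requires the first condition to be ignored, since every loss percentage above assumes that it is. That condition refers expressly to the number of retrieved dropouts, and 4 observations for three coefficients is a plain case of too few. Nor does the judgement need the results. Residual df depends on the total only, so a pooled count of people off treatment with a Day 84 value is enough, without treatment codes or LDL-C values.

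The remedy is not free either. A minimum of 5 mostly writes down what the gate already allows. A minimum of 6 or more replaces the imputation chosen for the treatment-policy estimand more often than the present wording does. The doubled-SD result also shows that no single cut-off is clearly right.

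**Conclusion.** No change follows. The observation is accurate: there is no stated minimum, and the convergence wording does not match a closed-form regression. Read as a whole, though, SAP 3.4.1 gives the analyst a condition based on the count and a named fallback. The limb about unobtainable estimates covers 3 or fewer retrieved dropouts or an empty arm. What the trigger alone misses, with a large effect, is one integer: exactly 4 with both arms represented. If the count condition were also disregarded there, roughly 29-30% of trials with 6 missing, or 46-49% with 15, would lose the primary test. No bias or Type I error inflation follows. At 5 the loss is about 2% with 15 missing, and about 11% in the less favourable run with SD 30 among retrieved dropouts.

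These sizes rest on the assumed baseline distribution, no retained effect off drug, and SD 15 unless stated. The documents give no basis for how often exactly 4 would occur. The sample code was re-implemented, not run in SAS, and the separate programming specifications were not available. What remains is a loosely worded condition that a competent analyst would apply sensibly, and a fixed count would bring a trade-off of its own.

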7.1 Lipid Profile/Biomarkers

Samples will be collected for the lipid profile/biomarkers at visits specified in the Schedule of Procedures ([Appendix A](#)). The lipid profile/biomarker samples will be analyzed for ApoB, HDL-C, LDL-C, non-HDL-C, TC, and TG. Samples should be collected while the participant is fasting (a minimum of 8 hours).

At Baseline (Visit 2), Day 84 (Visit 4), and Day 365 (Visit 7)/EOT/ET, LDL-C will be measured for all participants by preparative ultracentrifugation, also referred to as beta quantification. At all other scheduled visits, LDL-C will be calculated using the Friedewald equation unless $TG \geq 400 \text{ mg/dL} (\geq 4.52 \text{ mmol/L})$ or $LDL-C \leq 50 \text{ mg/dL} (\leq 1.30 \text{ mmol/L})$. If $TG \geq 400 \text{ mg/dL} (\geq 4.52 \text{ mmol/L})$ or $LDL-C \leq 50 \text{ mg/dL} (\leq 1.30 \text{ mmol/L})$, then LDL-C level will be measured directly by preparative ultracentrifugation.

All lipid profile/biomarker values will be blinded during the study through the EOS Visit (Visit 8). Participants, the Sponsor, Investigators, and all study site personnel involved in the study, including personnel carrying out study procedures, evaluating participants, entering study data, and/or evaluating study data, will remain blinded to lipid profile/biomarker values until all participants have completed the EOS Visit and the database has been locked for analysis.

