3.1.2 Analysis Visits

Scheduled visits will be assigned to analysis visits as recorded on the CRF.

For each analysis visit, if a scheduled visit occurs within the analysis day window, then the measurement from this scheduled visit will be used. If no scheduled visit occurs or laboratory results of the scheduled visit were unreportable, the unscheduled measurement closest to the target day will be used. If measurements are equidistant to the target day, the latter will be used. Otherwise, unscheduled visits will not be re-assigned and will remain labelled as unscheduled. If laboratory measurements for the scheduled visit were taken while a participant was not in a fasting state and laboratory measurements are available from an unscheduled visit during which the participant was in a fasting state (and the visit occurred within seven days of the scheduled visit), those fasted labs will be utilized in place of the unfasted labs.

Early termination (ET) visits will be assigned to analysis visits according to the following visit windows in Table 2:

Table 2 Analysis Visit Windows

Analysis Visit	Target Analysis Day	Low Analysis Day	High Analysis Day
Day 1 (Visit 2)	1	NA	NA
Day 30 (Visit 3)	30	2	57
Day 84 (Visit 4)	84	58	132
Day 180 (Visit 5)	180	133	225

Day 270 (Visit 6)	270	226	317
Day 365 (EOT)/(Visit 7)	365	318	N/A

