3.1.7 Evaluation of Site Effect

This is a multi-center study. Sites will not be pooled for any planned inferential analysis but may be pooled for subgroup analysis to assess the heterogeneity of treatment effects among pooled sites. The final pooling algorithm, if needed, will be specified before treatment unblinding and will be provided as an addendum to the SAP. Additionally, a review of by-site effects will be performed in the context of data listing review.

3.1.8 *Handling of Dropouts and Missing Data*

The objective is for missing data to be kept to a minimum. Continued efforts will be made to measure endpoints on all participants, including those who may have discontinued study drug. Accordingly, site investigators have been robustly trained about the importance of participant retention and multiple approaches will be implemented to retain participants who fail to actively maintain contact with the investigator.

Date Values

In cases of incomplete dates (e.g., AE, concomitant medication, and medical history start and/or stop dates), the missing component(s) will be assumed as the most conservative value possible. For example, if the start date is incomplete, the first day of the month will be imputed for the missing day and January will be imputed for the missing month. If a stop date is incomplete, the last day of the month will be imputed for the missing day and December will be imputed for the missing month. Incomplete start and stop dates will be listed as collected without imputation.

Date imputation will only be used for computational purposes such as treatment-emergent status. Actual date values, as they appear in the original CRFs, will be presented within the data listings.

Non-Date Values

For sensitivity analyses of the primary efficacy endpoint, missing values will be imputed using multiple imputation methods (see [Section 3.4.1](#)). For the analyses of secondary and exploratory efficacy endpoints, no imputation will be made for missing values. Safety data will be used according to availability, with no imputation for missing data.

3.1.9 *Laboratory Values Above or Below Limits of Quantification*

For laboratory values less than the lower limit of quantification (LLQ), half of the lower limit value (i.e., LLQ/2) will be used in the analysis. For values greater than the upper limit of quantification (ULQ), the upper limit value (i.e., ULQ) will be used in the analyses.

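### The primary Day 84 imputation fills missing values of participants still on treatment from treatment discontinuers, and its switch to the fallback has no usable donor rule

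*SAP*

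**What the plan says.** **Scope.** SAP 3.4.1, like Protocol 9.2.1.1, opens by saying that "missing measurements of non-retrieved dropouts will be modeled by known measurements from retrieved dropouts", within the same arm. The next paragraph gives the algorithm. Group 1 holds participants on treatment with an observed Day 84 value. Group 2, where imputation takes place, holds "either participants that had a missing value at Day 84, or participants that had discontinued treatment and had a non-missing value at Day 84". The note above the sample code repeats that only group 2 is used.

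**How a value can be missing on treatment.** Apart from a missed visit, SAP 3.4.1 accepts only an ultracentrifugation (PUC) result for the primary endpoint: "If the latter is not available, the LDL-C values will be assumed missing". SAP 3.1.2 allows an unscheduled sample as a substitute, but that helps only if PUC was run on it. Protocol 7.1 requires PUC for everyone at Visits 2, 4 and 7/EOT/ET; "At all other scheduled visits, LDL-C will be calculated using the Friedewald equation unless" a triglyceride or low-LDL-C condition is met.

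**Fallback.** The retrieved-dropout model is used where judged appropriate. The fallback replaces it when "model convergence is questionable and the given parameter estimates cannot be obtained". The fallback is the first sensitivity analysis, whose imputation group is "either participants randomized to the placebo treatment group, or participants that had a missing value at Day 84".

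**Early termination.** SAP 3.1.2 states: "Early termination (ET) visits will be assigned to analysis visits according to the following visit windows in Table 2". The Day 84 window is Days 58 to 132.

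**General missing-data section.** SAP 3.1.8 states: "For sensitivity analyses of the primary efficacy endpoint, missing values will be imputed using multiple imputation methods". It does not mention the primary analysis.

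**The concern.** The opening sentence and the algorithm name different recipients. Observed on-treatment values are set aside in group 1, so the only observed Day 84 values left in group 2 belong to discontinuers. Someone still taking obicetrapib with no Day 84 PUC result is imputed as if off the drug, which dilutes the estimated effect. The fallback imputes the same person from placebo.

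The trigger has a different fault. The coded method is a monotone regression, which is closed-form, so convergence is not something it can fail. Estimates fail to exist only when there are too few donors or an arm has none. Just above that point the model runs but is very unstable, and the text does not clearly call the fallback. The choice of primary method could then be made after the donor count is known. SAP 5.2 requires population exclusions to be settled before unblinding, but says nothing about this choice.

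**Working it through.** **1. The plan's own figure.** SAP 2.2.2 gives a 30-point effect, SD 15, 5% drop-out and 1-sided 0.025; allocation is 2:1. Evaluable: 300 × 0.95 = 285, or 190 and 95. SE = 15 × √(1/190 + 1/95) = 1.88, and 30/1.88 ≈ 16, so power is about 1.00. The stated figure of more than 90% holds with a wide margin.

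**2. Size of the dilution.** If k obicetrapib participants of 200 are missing while on treatment, and donors retain no effect, bias ≈ (k/200) × 30 points toward zero. The on-treatment missing rate is not in the documents; 1, 3 and 5% are assumed (k = 2, 6, 10).

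**3. Simulation of the coded steps.** Day 84 LDL-C is regressed on treatment and Baseline in group 2, with 100 imputations, ANCOVA with unequal variances and Rubin's rules. Assumed: 10+5 donors (obicetrapib + placebo), on-drug effect -30, off-drug 0, Baseline mean 120, SD 35, floor 70 mg/dL. There were 800 trials per row; Monte Carlo error is 0.06-0.09. True difference: -30 × 190/200 = -28.5.

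| Missing on treatment | Bias by arithmetic | As written | Split by treatment status | Fallback as written | Fallback with split |
|---|---|---|---|---|---|
| 1% | 0.3 | -28.1 | -28.4 | -28.3 | -28.5 |
| 3% | 0.9 | -27.7 | -28.5 | -27.6 | -28.4 |
| 5% | 1.5 | -26.9 | -28.4 | -27.0 | -28.6 |

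A repeat run at 5% gave -26.8, a bias of 1.7. SE is about 2 and power 1.00 throughout. If half the effect persists off drug, the truth is -28.5 - 15 × 10/200 = -29.25. The written rule at 5% then gives -28.6, a bias of 0.65.

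**4. Donor count.** The regression has three coefficients, so residual df = donors - 3. Four donors leave 1 df, and each variance draw divides by a chi-square on 1 df, which is often close to zero. With 15 values missing (1,500 trials per row):

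| Donors | Median SE | Power |
|---|---|---|
| 2+2 | 12.6 (90th percentile 85) | 0.53 |
| 3+1 | 14.8 | 0.49 |
| 3+2 | 3.1 | 0.98 |
| 4+2 | 2.5 | 1.00 |
| 4+3 | 2.3 | 1.00 |
| Fallback at 2+2 | 2.0 | 1.00 |

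Repeat runs at 2+2 with 15 missing gave power 0.50-0.58. With 15 stoppers in total, so 11 missing beside four donors, runs gave 0.55-0.74. Other assumed Baseline distributions (SD 25 or 50) barely change the results.

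**5. How likely this is.** This is a separate scenario from the table in step 4: 15 stop drug in total and 30, 50 or 70% are retrieved (assumed). The model cannot be fitted, so the fallback plainly applies, in 35, 4 and 0.1% of trials. It can be fitted but the test is non-significant in 7, 1 and 0%. If 30% of the remaining stoppers supply an early-termination value, the latter falls to 1.4, 0.3 and 0%.

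**6. SAP 3.1.8 against 3.4.1.** Section 3.4.1 and Protocol 9.2.1.1 make multiple imputation the primary analysis, and 3.4.1 lists observed cases as the third sensitivity analysis. Section 3.1.8 names only sensitivity analyses, then refers the reader to 3.4.1.

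**The case against.** The case for leaving this alone is fair on several counts. PUC is scheduled for everyone at Visit 4, so an attended visit without a result should be uncommon. The on-treatment missing rate is assumed, and the 5% row adds as much missingness as the whole planned drop-out. Early-termination donors may be sampled close to their last dose, so zero residual effect is the extreme case. The algorithm is stated in both text and code note, so a programmer knows what to run, and its bias is conservative. The instability is essentially a four-donor problem. Control-based, tipping-point and observed-case analyses are planned and would expose a distortion.

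Most of that stands, and it limits the severity. It does not remove the conflict between the stated scope and the algorithm. The SAP nowhere presents off-drug imputation of on-treatment participants as a deliberate conservative choice. The sensitivity analyses show robustness but do not decide which result is primary.

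A reader might infer that 3.1.8 labels the primary imputation a sensitivity analysis. It does not; it omits the primary analysis and points to 3.4.1, which is explicit.

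**Conclusion.** The concern holds as a specification fault of minor to should-fix weight. As written, missing Day 84 values of participants still on treatment are imputed from discontinuers or, under the fallback, from placebo. The bias is toward the null: about 0.3-1.7 points for assumed on-treatment missing rates of 1-5% with no off-drug effect, and less if some effect persists. The trigger is defective because the coded model yields estimates at four donors, where power is roughly 0.5-0.75 depending on the number missing. Section 3.1.8 is a wording inconsistency.

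Two stronger readings are not supported. One is that the estimand changes or that the dilution endangers the primary result: the treatment-policy estimand is unchanged, and power stayed at 1.00 with adequate donors. The other is that the trial has only about a 50% chance of success: that power is conditional on four donors, which is unlikely, and the retrieval rates behind any likelihood are assumptions. The textual findings are firm; the magnitudes depend on the stated assumptions.

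**What to change.** Before unblinding:

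1. Impute Day 84 values missing in participants still on treatment from on-treatment participants of the same arm, using Baseline LDL-C. Use the retrieved-dropout model only for off-treatment missing values. Keep the same split under the fallback.
2. Replace the appropriateness and convergence wording with a numeric minimum of donors, both arms represented, chosen by simulation. About 5-6 in total removes nearly all the power loss. State whether early-termination visits mapped to Day 84 count: the group 2 definition appears to include them, but the description of retrieved dropouts as people who remain in the study leaves doubt.
3. Add the primary analysis to the sentence in SAP 3.1.8.

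The cost is SAP wording and modest programming, with no new data. The fallback would be used more often. Taking retrieved donors as binomial with 15 stoppers and 30, 50 or 70% retrieval, the chance of falling below 5 is 52, 6 and 0.1%, and below 6 it is 72, 15 and 0.4%. The both-arms condition raises these figures, and early-termination donors lower them. A minimum of 7 would invoke the fallback in about 88, 29 and 2% of simulated trials. Going above 5-6 is thus a precision choice that more often displaces the protocol's retrieved-dropout method. If some effect persists off drug, the fallback is conservative.
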